11.1 Enrolment and randomisation

Once all required screening assessments are completed and eligibility is confirmed, participants will be registered with the Sponsor. Upon approval of registration, participants will be assigned a unique participant number that will remain consistent for the duration of the study.

Participants who sign an informed consent form, but do not fulfil the inclusion/exclusion criteria, will not be allocated a participant identification number.

Participants will be randomised into one of the following two groups on a 1:1 ratio with 500 participants per group:

- Group 1 (WLC): OM85 7.0 mg will be given daily for three months from Month 3
- Group B (Initial Treatment): OM85 7.0 mg will be given daily for three months from Day 0

Please see the Study Reference Manual for randomisation instructions.

11.2 Dosing, formulation and storage

OM85 (as Broncho-Vaxom adult capsules) is presented in a box with blister packs, containing 7.0 mg (30 doses). 7.0mg of OM85 is administered orally each day for 3 months.

Excipients: each capsule contains pregelatinised starch, magnesium stearate, anhydrous propyl gallate (E 310), monosodium glutamate, and mannitol.

The investigational product used throughout the study will be stored at the site's pharmacy in accordance with the instructions supplied by the Sponsor. Access to the investigational product will be restricted to authorised study staff only. OM85 (as Broncho-Vaxom adult capsules) will be kept below a temperature of 30°C. The product must not be frozen or refrigerated. The product should not be used for more than 3 months after opening.

11.3 Accountability for investigational product

Under Title 21 of the Code of Federal Regulations (21CFR 312.62), the site investigator is required to maintain adequate records of the disposition of the investigational product, including the date and quantity of product received, to whom the product was dispensed (participant-by-participant accounting) and a detailed accounting of any investigational product accidentally or deliberately destroyed.

All records regarding the disposition of the investigational product will be available for inspection by the monitor.

Participants will be requested to return all unused drug and empty blister packs & boxes at each visit. All efforts should be made by the site to follow up any bottles not returned.

11.4 Treatment adherence

The site will record the number of boxes dispensed to participants. Each box will have a unique identifying number. To enable the site to perform accountability, the participants will be asked to return all used and unused investigational product at each study visit. In the case where a participant is withdrawn from the study or becomes non-compliant with their allocated treatment, all efforts should be made to collect each previously dispensed study medication bottles. Dispensing and treatment compliance information will be recorded in the CRF.

11.5 Prohibited medications during study

There are no prohibited medications.

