Serious Adverse Event Reporting Children's Health and Environment Program, (CHEP)
Child Health Research Centre
[contact]

2. Investigator Signature Page

Reducing acute severe respiratory events in health care workers during the Covid-19 pandemic with OM85

I confirm that I have read **Protocol Version 2.0 dated 12th June 2020**. As the site investigator, I understand it, and I agree to adhere to the study conduct requirements and agree to conduct this protocol in accordance with International Conference on Harmonization Good Clinical Practice E6 (ICH-GCP), the Declaration of Helsinki, the United States (US) Food and Drug Administration (FDA), and local regulations and guidelines. I agree to report all information or data in accordance with the protocol and in particular I agree to report any serious adverse events. I will accept the monitors, auditors and regulatory inspector's oversight of the study. I will promptly submit the protocol to the applicable ethical review board.

Chief investigator signature

[name] [name]

Chief investigator printed name

Date

This page has been left blank intentionally

3. Synopsis of Protocol

Title	A phase 3, multi-centre study testing the reduction of acute severe respiratory events in health care workers during the Covid-19 pandemic with OM85
Clinical phase	Phase Three
Protocol number	BV-2020/19
Principal Investigators	[name] [name] [name] Assoc [name] [name] [name] [name] Assoc [name] [name] [name]
Statistical consultant	[name]
Study design	Parallel group, Wait-list design, with treatment delayed for 3 months Participants will be randomized on a 1:1 ratio with 500 participants per group in Australia and 500 per group in the UK. Group 1: Wait-list control. One capsule OM85 (7.0 mg) will be given daily for 3 months, commencing in Month 3, with 3 months follow-up off treatment. Group 2: Initial treatment. One capsule OM85 (7.0 mg) will be given daily for 3 months, commencing on day 0, with 3 months follow-up off treatment.
Accrual objective	2000 Health Care Workers (HCW):- 1000 from Brisbane Hospitals 1000 from UK Hospitals

Accrual period	4 weeks
Study duration	12 months
Countries	Australia, United Kingdom
Sites	Queensland Children’s Hospital, Brisbane (Site Investigator: [name]) Imperial College Hospital, London (Site Investigator: [name]) Prince Alexandra Hospital, Brisbane (Site Investigator: [name]) Princess Charles Hospital, Brisbane (Site Investigator: Assoc [name])

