6.1.4 Therapeutic options

As the PPE available to HCW is unlikely to prevent COV infection, an alternative approach is required. OM85, variably known as Broncho-Vaxom®, Broncho-Munal®, Ommunal®, Paxoral®, or Vaxoral®, has been in widespread clinical use throughout Europe and South America since the early 1980s for protection of infants, children and adults from the inflammatory sequelae of lower respiratory diseases, in clinical settings ranging from infection-associated wheeze in infants and school children^{6,7} to severe winter exacerbations occasioning hospitalization in adult COPD patients^{8,9}. While its mechanism-of-action is not fully understood, the accumulating body of clinical and experimental/mechanistic data has been sufficient to attract major support from regulators and funding agencies, exemplified by the US NIH-funded ORBEX RCT (NCT02148796) and NHMRC-funded OMPAC RCT (ACTRN12612000518864)⁷ which both target ARIs in children.

Evidence from numerous trials has demonstrated that OM85 treatment during periods of high infection risk can reduce the frequency of symptomatic ARI^{10,11}. The mechanism-of-action appears to involve reduction in susceptibility to upper respiratory infection and attenuation of the intensity of inflammation-associated symptoms that accompany infection spread to the lower airways. Clinical experience with OM85 indicates it is active against a wide spectrum of microbial pathogens. As such, it is likely to target immunoregulatory pathways that are fundamental to anti-microbial immunity¹⁰, particularly those which control the intensity of host defence-associated inflammatory responses. Accumulating evidence relating to COV pathogenesis suggests that primary infection followed by successful clearance represents the norm, with relatively rare severe infection-triggered events being associated with uncontrolled/excessive local and systemic inflammatory responses. Based on its performance in other infection-related settings^{6,10}, we hypothesize that OM85 pre-treatment has the capacity to enhance resistance to primary infection with COV, but more importantly to stabilize immunoregulatory mechanisms that maintain immune homeostasis during COV infection and lessen risk for progression to severe life-threatening symptoms.

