9.2 Exclusion criteria

Participants who meet *any* of these criteria are *not* eligible for enrolment:

- Staff with prior COV infection necessitating workforce removal

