11.6 Permitted medications during study

During the study, participants will be allowed to take medications routinely used in the management of fever, cough or wheezing attacks, including inhaled and oral steroids. All medications will be recorded in the source documentation and CRF.

12. Assessment of safety

The site investigator is responsible for the assessment and documentation of any event that meets the criteria of an AE (see Section 12.1) or an SAE (see Section 12.2).

AEs and SAEs will be collected from the time of first dose of investigational product until the participant has completed the study at their final visit, even if the participant ceases the investigational product prematurely.

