13.2.1 Analysis sample

All participants randomised who receive at least one dose of study treatment will be included in the "intention-to-treat" group for statistical analyses.

Participants who complete the treatment period and take at least 80% of scheduled doses will be included in the "per protocol" group for statistical analyses.

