13.3.1 Primary efficacy endpoint

The primary endpoint, defined in Section 7.2.1, will be analysed 3 months after enrollment using data collected prior to the WLC group commencing treatment, by comparing between-group differences in rates of ARI that necessitated workforce removal. The primary analysis will be conducted using log-binomial regression on both the "intention-to-treat" and "per protocol" groups.

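### The primary comparison needs wait-list controls free of OM85 in months 0–3, but no eligibility, medication or analysis rule says so

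*Combined protocol and SAP*

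**What the plan says.** The synopsis describes the design as "Parallel group, Wait-list design, with treatment delayed for 3 months". Section 11.1 assigns Group 1 to OM85 from Month 3 and Group 2 to OM85 from Day 0. No placebo is described, so controls will know that they are waiting. Section 13.3.1 analyses the primary endpoint "using data collected prior to the WLC group commencing treatment".

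Three places bear on exposure outside the allocation:

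- **Eligibility.** The single exclusion, in the synopsis and in section 9.2, is "Staff with prior COV infection necessitating workforce removal". Current or recent OM85 use is not mentioned.
- **Medication rules.** Section 11.5 reads "There are no prohibited medications". Section 11.6 adds "All medications will be recorded in the source documentation and CRF".
- **Analysis sets.** Section 13.2.1 defines the intention-to-treat group by receipt of at least one dose of study treatment. It defines the per-protocol group by completing the treatment period and taking at least 80% of scheduled doses. Neither definition mentions OM85 from another source.

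Section 6.1.4 lists five brand names and says that the product "has been in widespread clinical use throughout Europe and South America since the early 1980s". It does not mention availability in Australia or the UK.

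**The concern.** For months 0–3 the contrast is OM85 against no OM85. Any OM85 taken by controls in that window narrows it. Unallocated use can do this only from the control side, because Group 2 is already assigned the drug. If OM85 is effective, the estimated risk ratio moves towards 1 and power falls.

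Two routes are open on the text. A worker already taking OM85 can be enrolled and randomised to wait. A control who knows that treatment is 3 months away can try to get it elsewhere, and the only sentence in the protocol on barred medications bars nothing.

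If the trial then showed little difference, contamination could not be told apart from lack of effect unless exposure had been recorded systematically during those 3 months. That information is hard to recover later.

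**Working it through.** **1. Is there a safeguard elsewhere in the text?**

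- *Recording.* Section 11.6 requires all medications to be recorded, but the visit lists in section 10.2 and the rows of Appendix 1 contain no concomitant-medication item. The medical history in section 10.1.3 covers conditions, diseases, procedures and surgeries. Section 10.1.8 has medications reviewed by telephone only if required. Group 1 has no scheduled visit between Day 0 and Month 3.
- *Conduct.* Section 11.4 refers to participants who become non-compliant with allocated treatment, and section 15.4 defines violations and deviations broadly. Early OM85 use by a control could be classed under these, but no line does so. They do not reach a person already taking OM85 at entry, who is eligible under 9.2.
- *Analysis.* For Group 1, the scheduled doses counted in the per-protocol definition fall after Month 3. The 80% rule therefore cannot identify a control exposed in months 0–3. No planned analysis uses the medication record.

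**2. Reproducing the plan's power (section 13.2).** Inputs: control rate 20%, 1:1 allocation, alpha 0.05. Sidedness is not stated and two-sided is assumed. With control rate p1, treated rate p2 and mean rate m = (p1 + p2)/2, power is

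Φ{ [ (p1 − p2)√n − 1.96√(2m(1 − m)) ] / √( p1(1 − p1) + p2(1 − p2) ) }

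- 500 per group, 20% against 13.5%: 78.7%, against the stated 80%.
- 1000 per group, 20% against 15% (the stated 25% reduction): (0.05 × 31.623 − 1.96 × 0.5374) / 0.5362 = 0.985, so power is 83.8%. The stated 80% is conservative.

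**3. Effect of control uptake on the combined trial.** Let c be the share of controls taking OM85 for the full 3 months with the full assumed effect. The documents give no value for c, so the range below is an assumption.

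Control rate = (1 − c) × 20% + c × 15%. Apparent reduction = 1 − 15% / control rate.

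| c (assumed) | Control rate | Apparent reduction | Power, 1000 per group |
|---|---|---|---|
| 0 | 20.00% | 25.0% | 83.8% |
| 1% | 19.95% | 24.8% | 83.1% |
| 5% | 19.75% | 24.1% | 80.1% |
| 10% | 19.50% | 23.1% | 75.9% |
| 20% | 19.00% | 21.1% | 66.3% |

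Example at c = 10%: control rate 0.9 × 20% + 0.1 × 15% = 19.5%; reduction 1 − 15/19.5 = 23.1%; power Φ{(0.045 × 31.623 − 1.96 × 0.5343) / 0.5334} = Φ(0.705) = 75.9%.

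If use were confined to the UK half of the sample, 10% uptake there would be 5% overall, which is the 80.1% row.

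**The case against.** The case for leaving the plan alone has four parts.

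- **Early use is already a departure.** Group 1 is allocated OM85 from Month 3, participants must be judged able to comply with the protocol, and section 15.4 treats any failure to comply as a violation. Section 11.5 can be read as covering concomitant drugs, not as permission to start the trial drug early. This largely stands. A reader might infer from 11.5 that a control who buys OM85 complies fully and commits no deviation; sections 11.1, 11.4 and 15.4 do not support that. What remains is that the point is left to interpretation, and that current users at entry are not covered.
- **Availability is not documented.** A reader might infer from the reference to Europe in section 6.1.4, and from half the sample being recruited in the UK, that controls can readily obtain OM85. The section does not say so, and it names neither Australia nor the UK. Its examples of use are wheeze in infants and school children and exacerbations in adult COPD patients, not healthy staff. This stands, and uptake may be close to nil.
- **The loss is small at low uptake.** At 5% the combined trial still meets its own 80% target, and the figures assume full-effect use for the whole 3 months. This stands.
- **Intention-to-treat handling is right anyway.** Exposed controls belong in their randomised group, and the resulting bias is towards no effect. This also stands for the primary analysis. It does not answer the gap in the per-protocol set, or the lack of a scheduled question about use.

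**Conclusion.** The point holds as a cheap improvement to the plan. The primary contrast depends on controls being unexposed for 3 months; the eligibility criteria admit current users, section 11.5 bars nothing, and the per-protocol definition cannot remove a control exposed in that window. The recording rule in 11.6 is a partial safeguard only.

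The size is conditional. It rests on assumed uptake, on non-study OM85 having the full effect assumed in section 13.2, and on use throughout the 3 months. Under those assumptions power stays at about 80% or above up to 5% uptake and falls below it at 10% and 20%. If OM85 has no effect, control uptake does not bias the comparison.

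A reader might go further and infer that the control group is contaminated or that the trial is underpowered for this reason. The documents contain no evidence of uptake, so neither follows.

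**What to change.** Reconcile sections 9.2 and 11.5 with the allocation in section 11.1:

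1. In 9.2 and the synopsis, make current use of OM85 outside the study, under any of the brand names in 6.1.4, an exclusion. The sponsor sets the look-back period.
2. In 11.5, state that OM85 from outside the participant's allocation is not permitted in either group and that any use is a reportable deviation, recorded in the CRF with dates.
3. Ask about such use at existing contacts in months 0–3 (the messages or calls, and the Month 3 visit), on the same schedule in both groups. Asking only at unscheduled illness visits would make recording of exposure depend on the outcome.
4. In 13.2.1, keep exposed controls as randomised in the primary analysis, and remove controls exposed in months 0–3 from the per-protocol set. Report the number of users by arm.

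The cost is a few lines in an amendment, one added question, and the loss of any few workers who already take OM85. The CRF is already meant to hold medication data. The per-protocol removal is selection after randomisation, so that analysis should be read as supportive.

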11.6 Permitted medications during study

During the study, participants will be allowed to take medications routinely used in the management of fever, cough or wheezing attacks, including inhaled and oral steroids. All medications will be recorded in the source documentation and CRF.

12. Assessment of safety

The site investigator is responsible for the assessment and documentation of any event that meets the criteria of an AE (see Section 12.1) or an SAE (see Section 12.2).

AEs and SAEs will be collected from the time of first dose of investigational product until the participant has completed the study at their final visit, even if the participant ceases the investigational product prematurely.

12.1 Adverse events

In accordance with the TGA GCP guidelines (CPMP/ICH/135/95), an AE is any untoward medical occurrence in a participant administered a medicinal product and which does not necessarily have a causal relationship with this treatment. An AE can therefore be any unfavourable and unintended sign (including an abnormal laboratory finding), symptom, or disease temporally associated with the use of the investigational product, whether or not considered related to the investigational product.

All AE should be well documented in the participant's source notes and CRF. Start and stop dates, outcome and whether the participant required treatment will be recorded. The site investigator will determine the title of the AE, severity, relationship to investigational product and seriousness.

An AE does not include:

- Pre-existing disease or condition that was present prior to the first administration of the investigational product, and that does not have a clinically significant increase in severity and/or frequency during the study
- Medical or surgical procedures. The disease or condition that led to the procedure should be recorded as the AE, not the procedure itself.

AEs will be followed up until they have returned to baseline status or stabilised. Follow-up of AEs should continue until the overall clinical outcome has been ascertained or the final visit completed.

If an AE later escalates to meet the criteria for a SAE (see Section 12.2), then it must be reported to the Sponsor as an SAE. See Section 12.3 for Investigator's responsibilities for reporting SAEs.

12.1.1 Grading of adverse events

The severity of AEs experienced by study participants will be graded as mild, moderate, severe, life threatening or death by the site investigator.

12.1.2 Attribution of adverse events

The relationship, or attribution, of an AE to the investigational product will be determined by the site investigator. The relationship of the AE to the investigational product will be coded according to the following definitions:

Unrelated: The AE is due to an underlying or concurrent illness or effect of another drug and is clearly not related to the investigational product (e.g. has no temporal relationship to study drug or has a much more likely alternative aetiology).

Unlikely: The AE has little or no temporal relationship to the investigational product and a more likely aetiology exists.

Possibly: The AE has a strong temporal relationship to the investigational product and an alternative aetiology is equally or less likely compared to the potential relationship to the investigational product.

Probably: The AE has a strong temporal relationship to the investigational product or recurs on re-challenge. Another aetiology is unlikely or significantly less likely.

The site investigator should attempt to provide an alternative aetiology for all AEs considered to be unrelated, unlikely or possibly related to the investigational product. This will be recorded in the source documentation.

For the purposes of reporting to the relevant regulatory agencies, unrelated and unlikely AEs will be classified as Not Related, while possible and probably related will reported as Related.

12.2 Serious adverse events

12.2.1 Definition of serious adverse events

A SAE or reaction is any untoward medical occurrence that results in one or more of the following:

- results in death
- is life-threatening
- requires inpatient hospitalization or results in prolongation of existing hospitalization
- results in persistent or significant disability/incapacity
- is a medically important event or reaction

12.2.2 Clarification of serious adverse events

Death is an outcome of an AE and not an AE in itself.

A “life threatening” event is any adverse therapy experience that, in the view of the site investigator, places the participant at immediate risk of death from the reaction as it occurred.

An “inpatient hospitalisation” occurs when a participant is formally admitted to hospital for any length of time. It does not refer to Emergency Department or Accident & Emergency visits where the patient is observed and not admitted.

“Hospital in the home” or equivalent programs are not considered inpatient hospitalisations, and therefore do not need to be recorded as SAE’s.

Hospitalisations considered to be “routine” and therefore not SAEs will include hospitalisation for procedures unrelated to respiratory system or to the trial. Site staff will notify the Sponsor of routine hospitalisations within one week of the admission. Reporting instructions are provided in the Study Reference Manual.

If a routine hospitalization is prolonged due to an AE or results in any of the other definitions in Section 12.2.1, it should be reported to the Sponsor as a SAE.

Medical and scientific judgment should be exercised in deciding whether other situations than those listed in [Section 12.2.1](#) should be considered serious. This may include important medical events that might not be immediately life-threatening or result in death or hospitalization but might jeopardise the participant or might require intervention to prevent one of the other outcomes listed in Section 12.2.1.

Regardless of the relationship of the event to the investigational product, the event must be reported as a SAE if it meets any of the definitions listed in Section 12.2.1.

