6.3 Known and potential risks

Published clinical trials have reported OM85 to be well tolerated in children and adults. Reports of discontinuation of drug with an adverse event have been reported in three studies; two children from two separate studies discontinued drug due to rash or diarrhoea, and a study in adults with chronic obstructive pulmonary disease or chronic bronchitis reported 5 participants

in the active group (n=142) and 9 participants in the placebo group (n=131) discontinuing investigational product. In most clinical trials the number of participants experiencing adverse events were no different between the active (OM85) and placebo groups¹². In adults, the most common reported adverse events were gastrointestinal, including nausea and diarrhoea. Six studies reported no adverse events. In elderly patients (>65 years), the most common adverse events were disease of the genitourinary (19/147, 13%), “symptoms, signs and ill-defined conditions” (11/147, 7%) and disease of the circulatory system (7/147, 5%).

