12.4 Reporting to regulatory authorities

It is important that all known information at the time of the SAE is forwarded to the Sponsor within the protocol required time frame, as expedited reporting to the appropriate regulatory authorities may be required based on the following criteria:

No Reporting

This requirement applies if the SAE is deemed not serious by the Principal Investigators.

Standard Reporting

This requirement applies if the SAE is classified as any of the following:

- Serious, expected, and related to the investigational product
- Serious, expected and *not* related to the investigational product
- Serious, *unexpected* and *not* related to the investigational product

Expedited Reporting

This requirement applies if the SAE is classified as serious, unexpected and related to the investigational product. During these circumstances, the Sponsor must notify the appropriate health authorities within 15 days, however fatal or life-threatening events must be reported within 7 days.

13. Statistical considerations

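### Section 12.2.2 exempts admissions for non-respiratory procedures from SAE status without limiting this to planned admissions, which conflicts with 12.2.1, with its own last sentence and with 12.3

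*Combined protocol and SAP*

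**What the plan says.** Section 12.2.1 opens its definition with "A SAE or reaction is any untoward medical occurrence that results in one or more of the following", and one of the listed results is that the occurrence "requires inpatient hospitalization or results in prolongation of existing hospitalization". It sets no limit by organ system or by cause.

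Section 12.2.2 defines admission broadly: "An “inpatient hospitalisation” occurs when a participant is formally admitted to hospital for any length of time". It then carves out a class of routine hospitalisations, which do not count as SAEs and which take in "hospitalisation for procedures unrelated to respiratory system or to the trial". Sites notify the sponsor of these within one week of admission. A routine admission becomes an SAE if an AE prolongs it or if one of the other 12.2.1 criteria is met. The section closes with the opposite principle: "Regardless of the relationship of the event to the investigational product, the event must be reported as a SAE", provided that any 12.2.1 definition is met.

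Section 12.3 requires SAEs to be reported within 24 hours of site staff becoming aware, whatever the suspected cause, from informed consent onwards. It also requires the site investigator to notify the local ethics committee of SAEs.

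Section 12.1 says that a procedure is not itself an AE, but that the condition behind it is recorded as one. It excludes pre-existing conditions that have not become clinically significantly worse. Section 13.3.3 tabulates all reported AEs. Sections 10.1.9 and 12 start AE collection at the first dose.

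**The concern.** SAE status should follow from the outcome criteria in 12.2.1. The routine clause decides it by two other tests: whether the procedure concerns the respiratory system, and whether it is related to the trial. The last sentence of 12.2.2 rules out relationship as a deciding factor, and 12.2.1 has no organ-system test.

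Two sites could follow the protocol faithfully and classify the same admission differently. The SAE count would then depend partly on which sentence a site applied. The relatedness judgement would also be made by staff who can be expected to know the allocation, since section 8.1 describes immediate against delayed active treatment and no placebo. At stake are a consistent SAE count and the faster reporting that goes with SAE status.

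**Working it through.** No design figure is involved, so the check compares the rules on the same admissions. The clause's reference to the trial can mean unrelated to **both** the respiratory system and the trial, or unrelated to **either** one. Both readings are tested. All rows except the last are admissions for a procedure.

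| Admission | Routine clause, 'both' | Routine clause, 'either' | 12.2.1 and last sentence of 12.2.2 | Conflict |
|---|---|---|---|---|
| Planned, stable pre-existing condition, non-respiratory, unrelated to trial | Routine | Routine | Not an untoward occurrence, so no SAE | None |
| Unplanned, new condition, non-respiratory, judged unrelated to trial | Routine | Routine | SAE | On both readings |
| Unplanned, new condition, non-respiratory, judged trial-related | SAE | Routine | SAE | On 'either' only |
| Unplanned, new condition, respiratory, judged unrelated to trial | SAE | Routine | SAE | On 'either' only |
| Medical admission without a procedure | Outside the clause | Outside the clause | SAE if untoward | None |

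The second row settles the point: the conflict is there however the reference to the trial is read. The first and last rows show its limits.

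What a second-row admission loses if handled as routine, and what it keeps:

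1. **Classification.** It is not counted as an SAE.
2. **Timing.** Sponsor notice moves from 24 hours after awareness (12.3) to one week after admission (12.2.2). The two clocks start at different points, so the delay is not a fixed number of days.
3. **Ethics committee.** Notification under 12.3 is tied to SAEs and no longer applies.
4. **Escalation.** This needs prolongation by an AE or one of the *other* 12.2.1 criteria. The admission itself does not trigger it.
5. **AE record.** The underlying condition is still an AE (12.1) and is tabulated (13.3.3), but without its serious status.
6. **Wait-list participants before Month 3.** They have had no dose, so AE collection under 10.1.9 and 12 has not begun. Their daily symptom data cover respiratory symptoms only (10.1.7). An AE assessment is listed at their Month 3 visit, but the stated start of collection does not oblige it to reach back. SAE reporting from consent (12.3) would cover them, and this is the route that the routine clause closes.

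The number of events affected cannot be calculated, because the documents give no rate of procedural admissions.

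**The case against.** The strongest reply is that *routine* ordinarily suggests scheduled care, that 12.2.1 covers untoward occurrences rather than every admission, and that the protocol has several safeguards. Much of this stands. Excluding a planned admission for a stable condition contradicts nothing, only admissions for procedures are affected, and the safeguards are real. But the protocol says what it counts as routine, and neither planning nor pre-existence is part of it. The Study Reference Manual, which 12.2.2 cites for reporting instructions, may say more. It is not available here, and the protocol text should not need it to resolve a contradiction.

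Four stronger readings are tempting, and the documents do not support them.

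- *Events are hidden.* They are not: sponsor notice, escalation and AE recording remain, with the possible wait-list gap described above.
- *Events leave DSMB review.* Sections 8.3 and 15.5 give the board safety data and study data generally, with power to request more. Neither limits review to SAEs.
- *Harm is missed just where section 6.3 expects it.* That section says "In adults, the most common reported adverse events were gastrointestinal, including nausea and diarrhoea". These are adverse events, not serious events or procedures, and a medical admission for them falls outside the clause. Its figures for elderly patients transfer poorly to working hospital staff. The most that can be said is that a respiratory test of seriousness has no basis in the product's described adverse events.
- *Section 12.4 adds a second exemption.* Its no-reporting class reads "This requirement applies if the SAE is deemed not serious by the Principal Investigators". This concerns onward reporting to regulators and can sensibly be read as covering reports that turn out not to meet the criteria. It is at most a minor clarification.

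**Conclusion.** The conflict is real. It is confined to unplanned admissions for procedures that treat a new or worsened condition. For non-respiratory procedures judged unrelated to the trial it exists on either reading of the clause, and on the looser reading it extends further. The consequence is inconsistent SAE classification, slower sponsor notice and no ethics committee notification for those admissions. The AE backstop is weaker for untreated wait-list participants. The number of events cannot be given. The conclusion rests on the protocol text alone and assumes that the Study Reference Manual does not already restrict the routine class. The passages should be reconciled: the effect is probably modest, but a stated rule gives a wrong SAE count and is cheap to correct.

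**What to change.** In 12.2.2, limit routine hospitalisation to admissions planned before consent for a pre-existing condition that has not worsened, and delete the test based on organ system and relation to the trial. This matches the exclusion of unchanged pre-existing conditions in 12.1 and leaves 12.2.1, the last sentence of 12.2.2 and 12.3 consistent. The cut-off at consent is a proposal. Another definition of a planned admission would serve if it used neither organ system nor relatedness.

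For the change to reach wait-list participants before Month 3, the opening of section 12, which also starts SAE collection at first dose, should be aligned with the start at consent in 12.3. If 12.4 is being edited, its no-reporting class could be tied to reports that on review meet no 12.2.1 criterion.

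The cost is a wording amendment, matching instructions to sites, and a few more SAE forms.
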